**7.3 Dose Modifications**

**7.3.1 Dose Delay, Dose Modification and Stopping Rules during Dose Escalation**

[REDACTED]

[REDACTED]

[REDACTED]

[REDACTED]

[REDACTED]

[REDACTED]

[REDACTED]

Document Name: GCT1021-01 Protocol

Document Number: TMF-03326

Version: 11.0

### 7.3.2 Dose Modifications and Dose Delays for Patients Experiencing Adverse Events during Expansion

For patients who do not tolerate the protocol-specified dosing schedule, dose reductions are permitted in order to allow the patient to continue treatment with enapotamab vedotin.

Specific instructions on dose interruptions and reductions for different toxicities are provided in [Table 2](#), [Table 3](#) and [Table 8](#). These instructions are applicable for both the 1Q3W and 3Q4W dosing schedules and should be applied in association with the relevant dose modification scheme described in [Table 4](#) to [Table 7](#).

**Table 2. Instructions for dose interruptions and reductions for enapotamab vedotin related hematologic toxicity occurring during a cycle**

Hematologic Toxicity	Enapotamab Vedotin Dose Modification
Grade 4 neutropenia (ANC < 0.5 x 10  /L) or Febrile neutropenia (fever ≥ 38.5 C and ANC < 1 x 10  /L)	Enapotamab vedotin dosing should be interrupted until recovery to ≤ grade 2.  G-CSF therapy should be initiated and/or maintained, if already started, at the discretion of the treating physician.  On Day 1 of the next cycle, the dose of enapotamab vedotin may be maintained if neutropenia was the only AE, G-CSF treatments are continued or if event has normalized to grade 0 or baseline. Otherwise, decrease by one dose level at the start of the next cycle (see Table 4 , Table 6 and Table 7 ).
Grade 3 afebrile neutropenia	Repeat CBC with differential count weekly, consider dose interruption until recovery to ≤ grade 2, and G-CSF prophylaxis in case of worsening or delayed recovery beyond 2 weeks.
Grade 4 thrombocytopenia	Enapotamab vedotin dosing should be interrupted.  Decrease by one dose level when dosing is resumed (see Table 4 , Table 6 and Table 7 ).  To restart enapotamab vedotin treatment following a dose interruption, the platelets count must be ≥ 50 x 10  /L.
Other enapotamab vedotin related AEs (excluding neutropenia, febrile neutropenia, and thrombocytopenia) ≥ Grade 3	Enapotamab vedotin dosing should be interrupted.  Decrease by one dose level when dosing is resumed (see Table 4 , Table 6 and Table 7 ).

Document Name: GCT1021-01 Protocol

Document Number: TMF-03326

Version: 11.0

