### **2.3.2 Implications of Clinical Safety Results for Monitoring of Patients/Mitigation Plans**

Important newly identified risks for enapotamab vedotin include constipation, peripheral neuropathy and neutropenia.

In particular, events of constipation ( $\leq$  Grade 3), some of them leading to hospitalization, have been observed. The use of prophylactic concomitant medication to avoid and manage constipation is described in Section 7.4.1.

The peripheral neuropathy assessment through physical examination will be performed at the baseline and at End of Treatment visit, and the assessment will continue through the treatment period where indicated. Pausing of dosing or dose adjustment of enapotamab vedotin in case of neutropenia or peripheral neuropathy is required (please refer to Section 7.3.2). Specific safety reporting requirements are in place for AEs of peripheral neuropathy (please refer to Section 9.3.2).

Please refer to the IB for the benefit-risk of enapotamab vedotin.

Document Name: GCT1021-01 Protocol

Document Number: TMF-03326

Version: 11.0

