## 7.2 Dose-limiting Toxicity

For the purpose of dose-escalation, SAEs, non-serious (NS) ≥ Grade 3 AEs and clinically significant abnormal lab values at least possibly related to enapotamab vedotin will be collected and assessed by the DMC for DLTs (in each cohort during the first cycle; 21 days for the 1Q3W schedule and 28 days for the 3Q4W schedule). National Cancer Institute (NCI) Common Terminology Criteria for Adverse Events (CTCAE) v.4.03 will be used to assess severity of toxicities/AEs.

DLTs are defined as follows:

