### *Hematological*

- Grade 4 neutropenia (i.e., ANC < 0.5 × 10^9 cells/L) for minimal duration of 7 days.
- Grade 3 and 4 febrile neutropenia (i.e., ANC < 1.0 × 10^9 cells/L with a single temperature of > 38.3°C or a sustained temperature of ≥ 38°C for more than one hour).
- Grade 4 thrombocytopenia (≤ 25.0 × 10^9 platelets/L) for minimal duration of 7 days.
- ≥ Grade 3 hemorrhage associated with thrombocytopenia of ≥ Grade 3.
- Grade 4 anemia.

Document Name: GCT1021-01 Protocol

Document Number: TMF-03326

Version: 11.0

---

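### Table 2's fever cut-off for febrile neutropenia (≥38.5°C) is higher than the one in Section 7.2, so a narrow band of expansion events carries no instruction to interrupt dosing

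*Protocol*

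**What the plan says.** **Expansion dosing rule.** Section 7.3.2 introduces its tables with "Specific instructions on dose interruptions and reductions for different toxicities are provided in" Tables 2, 3 and 8. Row 1 of Table 2 covers Grade 4 neutropenia (ANC <0.5 x 10^9/L) or "Febrile neutropenia (fever ≥ 38.5 C and ANC < 1 x 10" (9/L follows). For either, dosing should be interrupted until recovery to Grade 2 or lower. There is no sustained-fever alternative.

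**DLT definition.** Section 7.2 lists "Grade 3 and 4 febrile neutropenia" as ANC <1.0 x 10^9/L "with a single temperature of > 38.3°C or a sustained temperature of ≥ 38°C for more than one hour". The section opens "For the purpose of dose-escalation".

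**Where the DLT criteria reach the expansion.** Footnotes 22 and 23 of Table 11 let a site skip the Day 8/15 visits (1Q3W) or the Day 22 visit (3Q4W) only if no adverse event met the DLT criteria in the previous two cycles, as judged by the investigator. Table 31 keeps this after Amendment 10.

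**The other visible rules.**
- Table 2, Grade 3 afebrile neutropenia: weekly blood counts and "consider dose interruption until recovery to ≤ grade 2".
- Table 2, last row: "Other enapotamab vedotin related AEs (excluding neutropenia, febrile neutropenia, and thrombocytopenia) ≥ Grade 3", for which dosing should be interrupted.
- Below Table 3: adverse events and grades not covered go to discussion with the medical monitor.
- Dose Delays: for toxicities that are not immune-related, dosing may be delayed for up to 12 weeks.
- Section 2.3.2: "Pausing of dosing or dose adjustment of enapotamab vedotin in case of neutropenia or peripheral neuropathy is required", with a cross-reference to Section 7.3.2.

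**The concern.** One protocol carries two fever cut-offs for febrile neutropenia, and the higher one decides whether an expansion patient's dose is held. An event can therefore be Grade 3–4 febrile neutropenia under Section 7.2, and serious enough to keep a monitoring visit in the schedule, without any row saying the next infusion should wait. No reason is given for 38.5°C.

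Neutropenia is named in Section 2.3.2 as an important newly identified risk, and Section 9.1.9.2 reports it in more than 20% of patients. On 3Q4W the drug is given weekly for three weeks, so the next infusion may be only 7 days away. What is at stake is an infusion given during an unresolved in-band event because the table did not ask for a pause.

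**Working it through.** The plan gives no figure on this point, so there is nothing to reproduce. The check compares the two rules as written, with T the temperature in °C and ANC in units of 10^9/L.

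**Rules**
- A (Section 7.2): ANC <1.0 and (single T >38.3, or T ≥38.0 for more than one hour).
- B (Table 2, row 1): ANC <0.5, or (T ≥38.5 and ANC <1.0).

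**Events that meet A but not B.** ANC <0.5 always meets B, which leaves ANC 0.5 to <1.0. T ≥38.5 also meets B, which leaves T <38.5.

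| Route into Section 7.2 | Band without a hold | Width | Values at 0.1°C resolution (assumed) |
|---|---|---|---|
| Single reading | >38.3 to <38.5 | 38.5 − 38.3 = 0.2 | 38.4 (1 value) |
| Sustained for more than one hour | 38.0 to <38.5 | 38.5 − 38.0 = 0.5 | 38.0, 38.1, 38.2, 38.3, 38.4 (5 values) |

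Coding both rules over ANC 0.1–1.1 and T 37.8–39.1 in steps of 0.1 gave the same temperatures, at ANC 0.5–0.9 only.

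**Events that meet B but not A, for ANC 0.5 to <1.0.** None: T ≥38.5 implies T >38.3. The fever arm of Table 2 lies wholly inside the Section 7.2 definition.

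**Does another visible rule hold an in-band event?**

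| Rule | Applies in the band? | Instruction |
|---|---|---|
| Table 2, Grade 4 or febrile neutropenia | No | Interrupt |
| Table 2, Grade 3 afebrile neutropenia | Only if the patient is read as afebrile | Consider interrupting |
| Table 2, Grade 4 thrombocytopenia | No | Interrupt |
| Table 2, Other, Grade ≥3 | No; excludes febrile neutropenia by name | Interrupt |
| Table 3 | No; non-hematologic toxicity | – |
| Table 8 | No; immune-related events | – |
| Medical-monitor clause | If no row applies | Discuss |
| Dose Delays | Yes | Delay permitted, up to 12 weeks |

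Three of the four rows in Table 2 instruct interruption, and an in-band event meets none of them.

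**The case against.** **The two rules have different jobs.** Section 7.2 defines first-cycle DLTs for escalation, while Table 2 manages expansion dosing. A reader might infer that the sections contradict each other; they do not, because neither claims to govern the other's decision. The objection is incomplete, though, because the visit-omission footnotes apply the DLT criteria to expansion patients in later cycles.

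**The band may already be covered.** Table 2 can be read as setting its own fever limit, so that Grade 3 neutropenia below 38.5°C falls in the afebrile row. That reading is reasonable, and it means the patient is not without guidance. It still yields only a suggestion to consider interruption. A reader might infer that dosing has to continue in the band. The documents do not support that: the investigator may delay, and the medical monitor is available.

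**The absence of a hold may be deliberate.** A reader might infer that every other related Grade ≥3 event is held. That is not so. Grade 3 thrombocytopenia has no hold, and thrombosis or embolism arising without adequate anticoagulation may continue without interruption. The fair comparison is only with events under the Other rows of Tables 2 and 3. Section 9.1.9.2 also records that most neutropenia events recovered without a dose change.

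**Section 2.3.2 does not add a hold.** A reader might take its requirement as a separate mandatory pause. It asks for pausing or dose adjustment and defers to Section 7.3.2 for the rule.

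**Safeguards exist.** Local hematology is reviewed before every infusion (Sections 8.5 and 16.3). The DLT-based footnotes keep the extra visits in place after an in-band event. Serious events are still reported within 24 hours (Section 17.3.1), although Amendment 10 ended Safety Reporting form submission for non-serious Grade 3 events. On 1Q3W there is often no dose left in the cycle to stop. All of this stands and limits the size of the point.

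**Conclusion.** The point holds as a minor inconsistency between definitions with a small safety consequence. For ANC 0.5 to <1.0 and a temperature that meets Section 7.2 but is below 38.5°C, no visible row says dosing should be interrupted. The consequence falls mainly on 3Q4W, which SAP Section 4.5.2 assigns to Cohorts 6 and 8.

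The documents do not say how many patients had such an event, and the temperature widths cannot be turned into a frequency. At protocol version 11.0 three patients remained on treatment, and the SAP addendum puts the last safety follow-up at 12 November 2021, so the practical reach is now mostly to any protocol that reuses this table. No endpoint is affected: the addendum's neutropenia category is built from MedDRA preferred terms, not from Table 2.

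Assumptions: the event is related to enapotamab vedotin, as Table 2 requires. The redacted text, including Tables 4–7, contains no further trigger; this is likely, since Section 7.3.2 places interruption instructions in Tables 2, 3 and 8 and sends the reader to Tables 4–7 for dose reduction. Table 2 says dosing *should* be interrupted, and that is the strength of instruction meant here.

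**What to change.** In row 1 of Table 2, replace the fever criterion for febrile neutropenia with the Section 7.2 definition: ANC <1.0 x 10^9/L with a single temperature >38.3°C, or ≥38°C for more than one hour. Leave the Grade 4 neutropenia arm as it is. The band is then empty, and no event now held loses its hold.

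The cost is a wording change in one table row, with no added tests. The downside is slightly more dose interruptions. In-band events would also come under row 1's re-dosing rule, which lowers the dose by one level at the next cycle unless its conditions for keeping the dose are met.

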**Table 3. Dose Modification for enapotamab vedotin related Non-Hematologic toxicity occurring during a cycle**

Non-Hematologic Toxicity	Enapotamab Vedotin Dose Modification
Thrombosis/embolism $\geq$ Grade 2	If the event occurred without or during inadequate anticoagulation, initiate adequate anticoagulation treatment. Enapotamab vedotin dosing may continue without interruption at the discretion of the treating physician. Dose level may be maintained at the discretion of the treating physician.  If the event occurred during adequate anticoagulation treatment (prophylactic dose of anticoagulation therapy with LMW heparin, heparin or Coumadin), discontinue enapotamab vedotin.
Peripheral Neuropathy = Grade 1 (only worsening from G0 to G1)	Enapotamab vedotin dosing should be reduced to a lower dose level as indicated in Table 5 , Table 6 and Table 7 without dose interruption.
Peripheral Neuropathy = Grade 2 or 3	Enapotamab vedotin dosing should be interrupted. Decrease dose (as indicated in Table 5 , Table 6 or Table 7 depending on dose and schedule (neuropathy must resolve to $\leq$ Grade 1).
Peripheral Neuropathy = Grade 4	Permanently discontinue enapotamab vedotin.
Other enapotamab vedotin related AEs $\geq$ Grade 3	Enapotamab vedotin dosing should be interrupted. Decrease by one dose level when dosing is resumed (see Table 4 , Table 6 and Table 7 ) (AEs must resolve to $\leq$ Grade 2).

For AEs and grades not addressed above, any dose modification must be discussed with the medical monitor.

Document Name: GCT1021-01 Protocol

Document Number: TMF-03326

Version: 11.0

In case dose reduction is required due to AE as per protocol (see [Table 2](#), [Table 3](#) and [Table 8](#)), the dose must be reduced according to the guidelines provided in [Table 4](#) to [Table 7](#) depending on the dose and dosing schedule as follows:

[Redacted]

**Table 4.** [Redacted]

[Redacted]

[Redacted]

**Table 5.** [Redacted]

[Redacted]

[Redacted]

**Table 6.** [Redacted]

[Redacted]

If 1.0 mg/kg dose cannot be tolerated by patient on the 1Q3W schedule (independent of type of AE), enapotamab vedotin should be permanently discontinued.

[Redacted]

Document Name: GCT1021-01 Protocol

Document Number: TMF-03326

Version: 11.0

---

**Table 7.** [REDACTED]

[REDACTED]

If 0.6 mg/kg dose cannot be tolerated by a patient on the 3Q4W schedule (independent of type of AE), enapotamab vedotin should be permanently discontinued.

Document Name: GCT1021-01 Protocol

Document Number: TMF-03326

Version: 11.0

---

### 7.3.3 Immune-related Adverse Events

Guidance for dose modification and management of immune-related AEs is provided in [Table 8](#). For Grade 1 immune-related AEs, enapotamab vedotin treatment should be continued with close monitoring. Corticosteroids taper should be initiated over the course of at least 4 to 6 weeks when the immune-related AE improves to  $\leq$  Grade 1. Trial treatment should be permanently discontinued for any serious Grade 3 immune-related AE that recurs and for any Grade 4 immune-related AE, with the exception of endocrinopathies that have been controlled by hormone replacement. For additional guidance on the recommended management of immune-related AEs, please refer to the *Management of Immune-Related Adverse Events in Patients Treated with Immune Checkpoint Inhibitor Therapy: American Society of Clinical Oncology Practice Guideline*.

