**Table 8. Dose Modification and Management of immune-related AEs**

Document Name: GCT1021-01 Protocol

Document Number: TMF-03326

Version: 11.0

Immune-related AEs	Toxicity grade (CTCAE v4.03)	Dose Modification	Guidance for Management of Immune-related AEs
Hepatitis (Elevated Liver Function Tests [LFTs]) Infliximab should not be used for management of Immune Related Hepatitis	Any Grade	-	
 
- Monitor and evaluate liver function test: AST, ALT, ALP, and TB.
 
- Evaluate for alternative etiologies (e.g., viral hepatitis, disease progression, concomitant medications).
 

	Grade 1 (AST or ALT > ULN to 3 x ULN and/or total bilirubin (TB) > ULN to 1.5 x ULN)	No dose modification If it worsens to Grade 2, refer to guidance for treatment of Grade 2 event	For Grade 1 AST or ALT and/or TB elevation: 
 
- Continue LFT monitoring per protocol.
 

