Pneumonitis	Grade 1-2	1st occurrence If there is radiographic evidence of pneumonitis progression, hold treatment until there is evidence of improvement/resolution to Grade 1 or less  2nd occurrence Permanently discontinue	Monitor for signs and symptoms of pneumonitis. Evaluate for pneumonitis with radiographic imaging. For $\geq$ Grade 2: Consider initiation of corticosteroid treatment (initial dose of 1-2 mg/kg prednisone or equivalent followed by taper). Corticosteroid taper should be initiated when the immune-related AE improves to $\leq$ Grade 1.
	Grade 3 or 4	Permanently discontinue	
Colitis	Grade 2	Continue treatment at the discretion of the investigator	Monitor for signs and symptoms of colitis. Consider gastroenterology consultation and confirm diagnosis of colitis. Consider administration of corticosteroids (initial dose of 1-2 mg/kg prednisone or equivalent) followed by taper. Corticosteroid taper should be initiated when the immune-related AE improves to $\leq$ Grade 1.
	Grade 3	Refer to text below	
	Grade 4	Permanently discontinue	
Type 1 diabetes mellitus (T1DM) or Hyperglycemia	Newly diagnosed T1DM or Grade 3-4 hyperglycemia	Refer to text below	Monitor for hyperglycemia or other signs and symptoms of diabetes. Consider endocrinology consultation. Consider administration of insulin for type 1 diabetes. Consider administration of anti-hyperglycemic in subjects with hyperglycemia.
Hypophysitis	Grade 2	Continue treatment at the discretion of the investigator	Monitor for signs and symptoms of hypophysitis. Consider endocrinology consultation. Consider administration of corticosteroids and initiate hormonal replacements as clinically indicated. Corticosteroid taper should be initiated upon immune-related AE improving to Grade 1 or less.
	Grade 3 or 4	Refer to text below	

Document Name: GCT1021-01 Protocol

Document Number: TMF-03326

Version: 11.0

Hyperthyroidism	Grade 2	Continue treatment at the discretion of the investigator	Monitor for signs and symptoms of thyroid disorders. Consider management with thionamides and beta-blockers as appropriate.
	Grade 3-4	Refer to text below	
Hypothyroidism	Grade 2	Continue treatment at the discretion of the investigator	Monitor for signs and symptoms of thyroid disorders. Consider endocrinology consultation. Consider initiation of thyroid replacement hormones per standard of care.
	Grade 3-4	Refer to text below	

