Nephritis and Renal dysfunction	Grade 1	Consider temporary hold pending consideration of baseline renal function and to confirm etiology 	Monitor for changes in creatinine levels. For $\geq$ Grade 2: If worsening or no improvement, consider administration of corticosteroids (prednisone 1-2 mg/kg or equivalent) followed by taper. Corticosteroid taper should be initiated upon immune-related AE improving to Grade 1 or less.
	Grade 2	Hold treatment until resolved to baseline 	
	Grade 3-4	Permanently discontinue	
Skin Toxicities	Grade 1-2	Continue treatment at the discretion of the investigator	Based on the severity of the adverse reaction, consider administration of corticosteroids. Corticosteroid taper should be initiated upon immune-related AE improving to Grade 1 or less.  For signs or symptoms of Steven Johnsons Syndrome (SJS) or Toxic Epidermal Necrolysis (TEN), withhold and refer the subjects for specialized care. If SJS or TEN is confirmed, permanently discontinue.
	Grade 3	Refer to text below	
	Grade 4	Permanently discontinue	
All other immune-related AEs	Grade 2	Continue treatment at the discretion of the investigator	Based on type and severity of AE, consider administration of corticosteroids. Permanently discontinue for any Grade 3 immune-related AE that recurs and for any life-threatening immune-related AEs.
	Grade 3	Refer to text below or discontinue based on the type of event.	
	Grade 4	Permanently discontinue	

1 20

Document Name: GCT1021-01 Protocol

Document Number: TMF-03326

Version: 11.0

---

[Redacted text block]

[Redacted text block]

[Redacted text block]

Document Name: GCT1021-01 Protocol

Document Number: TMF-03326

Version: 11.0

**Dose Delays**1Q3W and 3Q4W Schedule

For immune-related AEs, please refer to Section 7.3.3 regarding dose delays.

For all other AEs/Toxicities, enapotamab vedotin administration can be delayed for up to a maximum of 12 weeks. Radiological assessments should be continued during this period, as per protocol Section 8.4.7 and as clinically indicated, to monitor for disease progression.

Patients should be withdrawn from treatment if the treatment delay exceeds 12 weeks or if disease progression is observed while treatment is interrupted.

3Q4W Schedule Only

If a patient has to delay a dose for more than 14 days and the toxicity has resolved by that time, the patient should start with a new regular cycle upon resuming treatment.

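### Section 7.3.3 says to continue drug for every Grade 1 immune-related event, but Table 8 orders permanent discontinuation at a second Grade 1 pneumonitis

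*Protocol*

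**What the plan says.** The opening paragraph of Protocol Section 7.3.3 refers the reader to Table 8 for dose modification and management, then gives general rules. For the lowest grade the rule is "For Grade 1 immune-related AEs, enapotamab vedotin treatment should be continued with close monitoring". The same paragraph gives its own rule for stopping for good: a serious Grade 3 event that recurs, or any Grade 4 event, with an exception for endocrinopathies controlled by hormone replacement. Recurrent Grade 1 events are not on that list.

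Table 8 has one pneumonitis row for Grades 1 and 2 together and a separate row for Grades 3 and 4. For a first occurrence in the lower row it says: "If there is radiographic evidence of pneumonitis progression, hold treatment until there is evidence of improvement/resolution to Grade 1 or less". For a second occurrence it says: "Permanently discontinue". Nothing in the second-occurrence entry restricts it to Grade 2.

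Three other sentences bear on which rule governs:

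- Section 7.3.2 says that "Specific instructions on dose interruptions and reductions for different toxicities are provided in" Tables 2, 3 and 8.
- After Table 3: "For AEs and grades not addressed above, any dose modification must be discussed with the medical monitor".
- Under Dose Delays, after Table 8: "For immune-related AEs, please refer to Section 7.3.3 regarding dose delays".

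**The concern.** Two dosing rules in one section give opposite orders for the same event. A site that applies the Grade 1 sentence keeps a patient with recurrent pneumonitis on a drug that the table says to stop. A site that applies the table stops a drug that the text says to continue.

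The event was foreseeable here. Section 6.1 requires prior PD-1/PD-L1 treatment in Cohorts 2, 6 and 8. Exclusion criterion 6 in Section 6.2 admits patients whose earlier pneumonitis had fully resolved more than 6 months before. Appendix VI, as readable, replaces the trial-evaluation and adverse-event reporting sections but not Section 7.3.3, so version 11.0 still carries the conflict.

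What is at stake is consistent handling of a safety event across sites, not the validity of an analysis.

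**Working it through.** No arithmetic beyond counting applies, so the check sets the two sources side by side.

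**Step 1: which Table 8 entries address Grade 1.** The table covers ten event types: hepatitis, pneumonitis, colitis, type 1 diabetes or hyperglycemia, hypophysitis, hyperthyroidism, hypothyroidism, nephritis, skin, and all other. Four of them have a Grade 1 dose-modification entry.

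| Event type | Table 8 at Grade 1 | Against the text rule to continue |
|---|---|---|
| Hepatitis | "No dose modification If it worsens to Grade 2, refer to guidance for treatment of Grade 2 event" | Agrees |
| Skin (Grades 1 and 2 pooled) | Continuing is left to the investigator | No conflict |
| Nephritis | "Consider temporary hold pending consideration of baseline renal function and to confirm etiology" | Permissive, no conflict |
| Pneumonitis (Grades 1 and 2 pooled) | Hold or stop, depending on occurrence | See step 2 |

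So 1 of 4 Grade 1 entries can conflict.

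**Step 2: the three Grade 1 situations within the pneumonitis row.**

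- *First occurrence, no radiographic progression.* The table orders no hold. It agrees with the text.
- *First occurrence, radiographic progression.* The table orders a hold, released on improvement or on resolution to Grade 1 or below. An event already at Grade 1 meets the resolution limb from the outset; whether it must also improve is unclear. The cell carries a footnote that survives only as a bare number, apparently a literature reference. This is ambiguous and is not counted as a conflict.
- *Second occurrence.* The table says to stop permanently and the text says to continue. The second-occurrence entry has no footnote marker and no pointer to text below the table. This is a direct contradiction.

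Result: 1 of 3 situations clearly contradicts the text, 1 is ambiguous and 1 agrees.

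**Step 3: does the readable text settle which rule governs?**

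- The pointer in Section 7.3.3 calls Table 8 guidance. It does not say that the table overrides the sentence that follows.
- Section 7.3.2 calls the tables specific instructions on interruptions and reductions. It does not mention permanent discontinuation.
- The medical-monitor clause covers events and grades not addressed. Here the event is addressed twice.
- The dose-delay sentence sends the reader back to Section 7.3.3, which holds both rules.

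The first two favour the table. None states precedence.

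**The case against.** The strongest reply is that this is ordinary drafting: a general sentence followed by rows that refine it. Table 8 is also stricter than the text elsewhere, for example for Grade 3 pneumonitis and Grade 3 nephritis. A site would have to ignore the row written for the exact event in order to go wrong. Much of this stands, and most sites would probably follow the row. But the Grade 3 comparison does not carry over. There the text lists some events that require stopping and the table adds others. At Grade 1 the text positively tells the site to continue, so the table reverses it. Nor can a site assume that the table always prevails, because several of its rows defer to text below.

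A second reply is that the blocks redacted after Table 8 may contain the missing precedence rule. That cannot be excluded. The second-occurrence entry does not refer to that text, which makes an exception for it there less likely.

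A third is that the practical risk was low. Section 6.3.1 allows the investigator or sponsor to withdraw a patient on individual safety grounds, and a medical monitor was reachable at all hours (Section 17.7). The SAP addendum (Section 2.1) says immune-related events gave no clinically significant findings. All of this stands and limits the size of the point.

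A reader might also infer more than the documents support:

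- *That the first-occurrence hold is a second clear contradiction.* Its release condition and unreadable footnote do not allow that.
- *That the three patients on treatment at Amendment 10 are still at risk.* The addendum's end-of-trial date rules that out.
- *That discontinuation counts are biased.* Section 9.1.7 records the action actually taken, whichever rule the site followed.

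**Conclusion.** The inconsistency is real and minor. For a second Grade 1 pneumonitis the readable protocol gives two opposite orders and no stated way to choose between them. It affects one of four Grade 1 entries in Table 8 and, within that entry, one of three situations clearly.

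The number of patients who had a recurrent Grade 1 pneumonitis is not stated, so the past impact cannot be sized. Three patients were on treatment when version 11.0 was issued on 30 June 2021. None remains exposed after 12 November 2021, the last patient's end of safety follow-up in Section 2.1 of the SAP addendum. Sample size, error rates and reported estimates are untouched.

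The conclusion rests on two assumptions: that the redacted blocks hold no rule on precedence, and that the pooled row label means what it says, so that Grade 1 belongs in it. If the second-occurrence entry is read as a second episode with radiographic progression, the conflict narrows further but does not disappear.

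**What to change.** Add *unless otherwise specified in Table 8* to the Grade 1 sentence in Section 7.3.3. This settles precedence in favour of the more cautious row and leaves the hepatitis, skin and nephritis entries as they are.

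It needs no new procedure. The downside is a few more discontinuations for recurrent Grade 1 pneumonitis at sites that would have followed the text. Because the change affects treatment, Section 12.3 requires prior ethics and regulatory approval, across the six countries listed in Section 11.1. While the trial was running, it would have been proportionate to bundle it with another amendment. With follow-up ended, the correction has no remaining patient to protect here; its use is in any later protocol that reuses this section.
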